
KEY PERSONNEL (List names of all investigators including PI and their respective specialties)

Name	Professional Discipline/ Specialty	Role in the Project
1. [name]	Assistant Scientist / Immunology	Principal Investigator
2. [name]	Head, CHP/ Epidemiology	Co- Principal Investigator
3. [name]	Head, MHRP/ Epidemiology	Co-investigator
4. [name]	Associate Scientist / Epidemiology	Co-investigator
5. [name]	Senior Scientist / Immunology	Co-investigator
6. [name]	Division Director, CSD/ Nutrition	Co-investigator

DESCRIPTION OF THE RESEARCH PROJECT

Hypothesis to be tested:

Concisely list in order, in the space provided, the hypothesis to be tested and the Specific Aims of the proposed study. Provide the scientific basis of the hypothesis, critically examining the observations leading to the formulation of the hypothesis.

A. Long term supplementation of iron and/or zinc or micronutrient mix in infants six months onward will:

1. increase the levels of total IgA levels in serum (in infants who will receive zinc alone) and s-IgA in stool (in infants who will receive zinc alone or iron alone or in combination)
2. increase specific IgG response against vaccines (measles or oral polio vaccine) (in infants who will receive zinc alone or iron alone or in combination)
3. improve cellular immune status by enhancing the proliferative response against mitogen (PHA) and response against multiple antigens (in infants who will receive zinc alone or iron alone or in combination)
4. enhance the numbers of Pan T cells (CD3), T helper cells (CD4) (in infants who will receive zinc alone) and natural killer cells (CD56 / CD16) (in infants who will receive iron alone) in systemic circulation
5. activate complement components in blood (in infants who will receive zinc alone)

B. Infants who will receive the micronutrient mix will have an overall positive effect on the immune status as described above.

Specific Aims:

Describe the specific aims of the proposed study. State the specific parameters, biological functions/ rates/ processes that will be assessed by specific methods (TYPE WITHIN LIMITS).

To study the following before and 6 months after supplementation:

1. The levels of total and specific IgA (response against measles/oral Polio vaccine) in serum and secretory IgA in stool.
2. To study the proliferative responses of lymphocytes to mitogens and to measure IL-2 levels in the culture supernatant.

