Infants from selected Matlab villages meeting the inclusion and exclusion criteria as given in the original protocol will be enrolled in the parent study. In addition to the criteria set for the original protocol, subjects who develop any infection including ARI or diarrheal diseases will be excluded from the proposed study since the infection may have an effect on the immune responses of these subjects.

Outcome Variables and Sample size Determinants

The following outcome variables will be measured:

- | | | |
|------|-------------------------|---|
| (i) | Humoral responses: | IgA in serum
Serum IgG responses to measles/Polio vaccines
sIgA in stool

Complement components C3 and C5 in serum |
| (ii) | Cell mediated immunity: | Proliferative response of peripheral lymphocytes to mitogens
Interleukin 2 in culture supernatant of proliferative lymphocytes
Phenotypic changes in the peripheral blood |

Table 1. Sample size calculations:

Outcome variables	Expected levels in the control group	Expected level in the treatment group (expected % improvement/reduction)	*Sample size required in each group	References
1. IgA in serum, mg/L	81±32	111±26	19	17
2. s-IgA in stool, g/L (for zinc)	0.05±0.01	1.1±0.45	3	36
3. s-IgA in stool, mg/dl (for iron)	0.05±0.01	7.4±0.25	2	27
4. Antibody titers against Polio virus vaccine	169	346	99	33
5. [§] Response to PHA	31±9	58±13	4	17
6. IL-2 in culture supernatant, units/ml	106.5±99	137.3±67	149	28
7. CMI, % of anergic children	67%	47%	131	15
8. Phenotypic changes	0.43±0.53	2.09±1.68	12	28
a) CD3				
b) CD4	0.30±0.39	1.43±1.24	14	28
c) CD8	0.13±0.17	0.76±0.54	9	28

[§]Stimulation index, mean±SD. A loss of follow-up of 20% has been included. *Sample size required in each group of infants supplemented with either zinc alone or iron alone, or zinc and iron in combination or the multimix. Allowance for 10% drop-out has been made. Since sample size is different for each variable, for convenience we decided that for variables 1, 2, 3, 5, and 8, sample size is 20. Sample size for variables 4, 6 and 7 will remain the same as shown in the table.

Methodology

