In the original project, blood (3 ml) samples will be collected before micronutrient supplementation and 6 months later. In the present proposal, additional 1ml of blood will be collected at the same time points, therefore the total blood volume will be 4 ml. Mononuclear cells will be separated from total blood and used for various purposes. Stool samples will be collected at the time of blood collections.

Blood:

Lymphocytes

Blood (4 ml) will be collected in heparinized tubes. Lymphocytes separated from venous blood upon Ficoll-Hypaque separation will be used for proliferation response to mitogens (PHA) and for phenotyping of lymphocytes by flow cytometry. Lymphocytes will be frozen and carried in

liquid nitrogen to the Karolinska Institutet at the Division of Infectious Diseases, Huddinge University Hospital where phenotyping will be performed.

Plasma

Total IgA contents will be determined in plasma using ELISA with pooled human Swedish milk with a known IgA concentration of 1 mg/ml as a standard (34). In brief, Nunc plates will be coated with affinity pure goat antihuman IgG as a concentration of 1 µg/ml in PBS(phosphate buffered saline) (100 µl/well).and incubate the overnight at room temperature. Plates will be washed 2 times with PBS and blocked with 1% BSA-PBS (bovine serum albumin-phosphate buffered saline) (200 µl/ml) and will be incubated for 30 min at 37°C. After incubation, plates will be washed 3 times with PBS-Tween and once with PBS. Standard Swedish milk (2 µg/ml) and samples (100 µl/well) will be added to the specific wells. In case of samples initial dilution will be 1: 500 and then 3 fold serial dilution continued. . Plates will be incubated for 90 minutes at room temperature. After washing as above, conjugate Goat anti human-IgA-HRP (horse radish peroxidase) (1:4000 in 0.1% BSA-PBS-Tween, 100 µl/well) will be added and incubated for 1 hrs in room temperature. After washing 3 times, OPD substrate will be added and plates will be read after 20 minutes of development at 450nm.

Antibody titers to measles immunization will be carried out using ELISA (31). Complement C3 and C5 in plasma will be measured using commercially available kits (Amersham Pharmacia Biotech, England). IL-2 will be measured in the culture supernatant from mitogen-stimulated cells after proliferation using commercially available kits (R&D Systems, Minneapolis, USA).

Stool

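### Table 1 keeps IL-2 at 149 infants per group, but only about 80 per group give venous blood, and the PHA proliferation read-out from the same culture step is set at 20

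*Protocol*

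**What the plan says.** Table 1 (Protocol, Outcome Variables and Sample size Determinants) lists a required size of 4 per group for the response to PHA and 149 per group for IL-2. The footnote, which gives convenience as the reason for a common size, then reads "for variables 1, 2, 3, 5, and 8, sample size is 20. Sample size for variables 4, 6 and 7 will remain the same as"; the tabled values are meant. So PHA proliferation is fixed at 20 per group and IL-2 at 149.

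The two read-outs share a culture step. The outcome list gives "Interleukin 2 in culture supernatant of proliferative lymphocytes". The Methodology section (Plasma) says "IL-2 will be measured in the culture supernatant from mitogen-stimulated cells after proliferation". Specific Aim 2 pairs them: "To study the proliferative responses of lymphocytes to mitogens and to measure IL-2 levels in the culture supernatant". PHA is the only mitogen named, and no separate culture for IL-2 is described.

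The blood supply is stated elsewhere. The background section and the abstract for the ethical review committee describe 800 infants randomised to five groups, with venous blood taken from 50% of them at the start and end. The last ethics item repeats the 50% for the enlarged 4 ml sample that includes this addendum's extra 1 ml.

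The footnote also gives two loss allowances: "A loss of follow-up of 20% has been included" and "Allowance for 10% drop-out has been made".

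**The concern.** Two outcomes that depend on the same cultured lymphocytes have fixed sizes about seven-fold apart, and the larger exceeds the number of infants who are bled. The protocol does not say how many infants per group have cells cultured, or how the 20 for proliferation are picked from them.

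At stake is the IL-2 comparison. Table 1 implies conventional power for it, and a reader would take that at face value. If the study runs as the venous sampling allows, a null IL-2 result would be far less informative than the table suggests. A lesser matter is proliferation (hypothesis A3): its precision would be lower than the cultures being run could give.

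**Working it through.** **Inputs**
- IL-2, Table 1: control 106.5 (SD 99), treated 137.3 (SD 67) units/ml; difference 30.8.
- PHA stimulation index, Table 1: control 31 (SD 9), treated 58 (SD 13); difference 27.
- Venous sample: 50% of 800 infants, five groups. Equal allocation is assumed.
- Level and power are not stated. Two-sided 5% and 80% are assumed and tested first against the table.

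**1. Reproduce the 149.**
n = (1.96 + 0.842)² × (99² + 67²) / 30.8² = 7.85 × 14,290 / 948.6 = 118.2, so 119 per group. Allowing for 20% loss, 119 / 0.80 = 148.75, so 149: an exact match. A 10% allowance would give 133, and 90% power with 20% loss would give 199. The same settings reproduce the tabled sizes for serum IgA (19), s-IgA (3 and 2), PHA (4), CD3 (12), CD4 (14) and CD8 (9). The table therefore rests on a two-sided 5% level, 80% power and 20% loss.

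**2. Infants available.**
0.50 × 800 = 400 bled; 400 / 5 = 80 per group. This is below both 149 and the 119 completers that 149 is meant to secure. With 10% loss 72 remain, and with 20% loss 64. The addendum's exclusion of infants who develop infection could lower this further; the protocol gives no rate for it.

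**3. IL-2 power at the sizes in play.**
SE = √(14,290 / n). Power comes from the noncentral t distribution with unequal variances. The detectable difference is 2.80 × SE (80% power, normal formula).

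| n per group | SE | Power for 30.8 | Detectable difference |
|---|---|---|---|
| 119 | 10.96 | 80% | 30.7 |
| 80 | 13.37 | 63% | 37.4 |
| 72 | 14.09 | 58% | 39.5 |
| 64 | 14.94 | 53% | 41.9 |
| 20 | 26.73 | 20% | 74.9 (about 77 with the t correction) |

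**4. PHA at 20 and at 80.**
SE of the difference = √((9² + 13²) / n) = √(250 / n). At n = 20 it is 3.54, against a planned difference of 27, and power is above 99.9%. At n = 80 it is 1.77, half as large.

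**5. Readings.**
Thymidine uptake in 20 infants × 5 groups × 2 visits = 200 readings. In 80 × 5 × 2 = 800.

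**The case against.** The strongest reply is that the footnote leaves IL-2 at 149, so nothing in the protocol caps cultures at 20. That is right. A reader might infer that IL-2 would have only about 20% power, but this follows only if cultures were limited to the 20 infants set for PHA, and the footnote does not say so.

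It is also fair to say that measuring uptake in 20 infants is ordinary nested sampling. Thymidine uptake and the IL-2 kit are separate read-outs, and 20 per group is ample for the planned PHA effect. A reader might infer that proliferation data are thrown away; they would simply not be read. A reader might also take the words about convenience to describe how infants are picked. In context they describe setting several small requirements (2 to 19) to a common size. How the 20 are selected is not stated, so no selection bias can be claimed. Nor does the protocol give the number of wells per infant, so a single shared culture is an inference; what it does tie together is the culture step.

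A further reply is that the Data Analysis section plans a pre/post Wilcoxon signed-rank test, which may need fewer infants. The documents give no within-child correlation. Taking Table 1's two SDs as pre and post SDs, the SD of the change is √(14,290 − 2 × ρ × 99 × 67): 119.5 for ρ = 0 and 87.5 for ρ = 0.5. A paired t test then has about 62% to 87% power at 80 infants and 53% to 79% at 64. So a within-group test might do better, depending on an unstated correlation. But Table 1 sizes treated against control, and its 149 would still not be reached.

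None of this answers the limit of about 80 per group.

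**Conclusion.** The point holds in this form: the 149 per group for IL-2 cannot be delivered from a venous sample of about 80 per group, and the protocol does not reconcile it with the 20 set for proliferation from the same culture step. IL-2 power for the planned difference is at most about 63%, and about 53% after 20% loss, against the 80% that the table implies. The cost on the PHA side is precision only.

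This rests on equal allocation to five groups, a two-sided 5% level inferred from the table, and a between-group comparison of means with Table 1's SDs. Infection exclusions would lower the figures; a strong baseline correlation, if used in the analysis, would raise them.

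**What to change.** - State one number of infants per group whose lymphocytes are cultured, applying to variables 5 and 6 and no larger than the roughly 80 per group who are bled.
- Replace 149 for IL-2 with that number. Give the resulting power for 30.8 units/ml, or the detectable difference (about 37 units/ml at 80 per group, about 42 at 64).
- Read thymidine uptake in every culture run for IL-2. If uptake is kept to 20 per group, say so and state how the 20 are selected.
- Keep one loss allowance; the tabled sizes match 20%, not 10%.

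The wording changes cost nothing beyond a less favourable IL-2 figure. Reading uptake in all cultures needs no additional infants, blood or cultures beyond those run for IL-2, but it does need reagent and counting: about 800 readings instead of 200 at 80 per group. The budget has USD 5,000 for thymidine and cell-culture reagents together, so whether this fits should be checked before committing.

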3. Multitest CMI skin test will be performed to study the cell-mediated immune response in infants.

4. To study phenotypic changes in the peripheral blood mononuclear cells.
5. To study the complement response (C3, C5) in infants.

Background of the Project including Preliminary Observations

Describe the relevant background of the proposed study. Discuss the previous related works on the subject by citing specific references. Describe logically how the present hypothesis is supported by the relevant background observations including any preliminary results that may be available. Critically analyze available knowledge in the field of the proposed study and discuss the questions and gaps in the knowledge that need to be fulfilled to achieve the proposed goals. Provide scientific validity of the hypothesis on the basis of background information. If there is no sufficient information on the subject, indicate the need to develop new knowledge. Also include the **significance and rationale** of the proposed work by specifically discussing how these accomplishments will bring benefit to human health in relation to biomedical, social, and environmental perspectives. (DO NOT EXCEED 5 PAGES, USE CONTINUATION SHEETS).

Original protocol:

The above study (entitled "A community-based, randomized, controlled trial to assess the efficacy of iron and / or zinc or a micronutrient mix supplementation to reduce anemia and morbidity and to improve growth and development in Bangladeshi infants") (Protocol #99-014) is a community based, double blind, randomized, controlled trial to evaluate the efficacy of weekly supplementation of iron and / or zinc or a micronutrient mix for six months in infants beginning 6 months of age. Five groups will be studied. (i) 20 mg iron with 1 mg riboflavin, (ii) 20 mg zinc with 1 mg riboflavin, (iii) both iron and zinc with riboflavin, (iv) a micronutrient mix (UNICEF mix), and (v) riboflavin only (placebo) will be studied.

The outcome variables that will be measured are: (a) iron status, (b) zinc status, (c) copper status, (iv) diarrheal morbidity, (v) growth, and (f) cognitive, psychomotor and behavioural development. Eight hundred infants will be selected from the Matlab villages and will be enrolled in the study over a period of six months. Selection criteria are described in the original

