Immunological assays including enzyme linked immunosorbant assays (ELISA), lymphocyte proliferation assay, will be carried out at ICDDR,B since the techniques have been standardized and the equipment needed for carrying out the assays are available in ICDDR,B. However, to perform sterile work, a biohazard hood will be required at Matlab. For separating lymphocytes from blood, a refrigerated table-top-centrifuge will also be needed at Matlab. An ultra low freezer (-80° C) will be required to store lymphocytes after separation from whole blood. These lymphocytes will be phenotyped later by flow cytometry. Since fluorescent associated cell sorter (FACS) is not available at ICDDR,B, frozen cells have to be carried in dry ice (-70° C) to Sweden. FACS will be available to the PI to perform flow cytometric assay (phenotyping) at the Division of Infectious Diseases, Karolinska Institutet, Sweden.

Data Analysis

Describe plans for data analysis. Indicate whether data will be analyzed by the investigators themselves or by other professionals. Specify what statistical softwares packages will be used and if the study is blinded, when the code will be opened. For clinical trials, indicate if interim data analysis will be required to monitor further progress of the study. (TYPE WITHIN THE PROVIDED SPACE).

Baseline characteristics of the different supplementation/treatment and comparison groups will be examined for group comparability as described in the original protocol.

To examine the effect of individual micronutrient i.e. zinc or iron on the immune parameters between the pre and post supplementation days, Wilcoxon-signed Rank test will be used. To examine the proportion of subjects responding to a particular supplement, Chi-square test will be performed. To examine the potential additive and multiplicative effects of providing zinc, iron and other micronutrients on the immune parameters, multiple regression analyses will be performed.

Ethical Assurance for Protection of Human Rights

Describe in the space provided the justifications for conducting this research in human subjects. If the study needs observations on sick individuals, provide sufficient reasons for using them. Indicate how subject's rights are protected and if there is any benefit or risk to each subject of the study.

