Funding Source: Being sought

Direct Cost: 68,800 US\$

Starting Date: As soon as possible

Closing Date: One year from starting

Sl. No	Account Description	Position	Salary Support		
			Effort %	Salary	One Year
1	[name]	NOB	25	970	3,000
4	Research Officer, at ICDDR,B	GS-5	100	349	4,200
5	Research Officer, at Matlab	GS-5	40	349	1,700
6	Lab attendant	GS-1	100	170	2,400
	Sub Total				11,300
	Travel				
8	International Travel (trip to KI)				5,000
	Sub Total				5,000
	Laboratory Analysis				
9	Immunological Assays				
	Ficoll-hypaque blood separation, buffers				1,000
	Complement and IL-2 cytokine ELISA kits				5,500
	Mitogen, antigens, monoclonal antibodies for flow cytometry				4,000
	Reagents for thymidine uptake assay, cell culture reagents etc				5,000
	Antibodies, and reagents for ELISA				4,500
10	Laboratory Supplies				
	Plasticware, glassware, Chemicals and media, ELISA plates, stool extraction tubes, sterile microfilters etc				5,000
	Sub Total				25,000

	Other Contractual Services	One Year
14	Printing and Publication	1,500
	Communication, repair, maintenance	800
15	Dry ice and freight charges	1,000
	Sub Total	3,300
	Interdepartmental Services	
16	Pathological Tests	600
17	Microbiological tests	600
18	Biochemistry Tests	500
	Sub Total	1,700
24	Capital Expenditure	
	Table-top centrifuge, refrigerated	7,500
	Biohazard hood	10,000
	Ultra low Freezer, -83° C	5,000
	Sub Total	22,500
	TOTAL DIRECT COST	68,800

Budget Justifications

Please provide one page statement justifying the budgeted amount for each major item. Justify use of man power, major equipment, and laboratory services.

Two research officers are needed, one for the Matlab lab (40%) and one for the Immunology lab (100%) in ICDDR,B to carry out immunological assays. A lab attendant will be required at the Dhaka lab.

Capital equipment cost includes a table top refrigerated centrifuge, a biohazard hood and an ultra low freezer (-83° C). The table top refrigerated centrifuge will be needed for separating lymphocytes from blood. The biohazard hood will be required to perform sterile work including cell proliferation assay. The ultra low freezer will be required to store lymphocytes. These lymphocytes will be phenotyped later by flow cytometry. These pieces of equipment are essential for carrying out immunological assays in Matlab laboratory. Once this laboratory is equipped, it will be possible to carry out future immunological studies including vaccine immunogenicity studies in Matlab.

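### The transport medium for the phenotyping cells is contradictory, and the within-group before/after test cannot separate a supplement effect from a storage or assay-run effect

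*Protocol*

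**What the plan says.** The Lymphocytes paragraph of the protocol's Methodology section has the separated cells frozen and taken in "liquid nitrogen to the Karolinska Institutet at the Division of Infectious Diseases" for phenotyping. Facilities Available describes the same cells, journey and assay differently: "frozen cells have to be carried in dry ice (-70° C) to Sweden". On storage before the journey, that section says "An ultra low freezer (-80° C) will be required to store lymphocytes after separation from whole blood".

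The Detailed Budget follows the second account. It has a -83° C freezer and a line for "Dry ice and freight charges", and nothing for liquid nitrogen. Travel appears once, as "International Travel (trip to KI", and Budget Justifications ties it to the flow cytometry without giving a number of journeys.

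On timing, Facilities Available says only "These lymphocytes will be phenotyped later by flow cytometry". Methodology says blood "samples will be collected before micronutrient supplementation and 6 months later". In the parent study, infants "will be enrolled in the study over a period of six months".

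Data Analysis assigns the effect of zinc or iron alone to a Wilcoxon signed-rank test between the days before and after supplementation. Multiple regression is reserved for additive and multiplicative effects of the nutrients. The design includes a randomised, blinded, riboflavin-only placebo arm. The note to Table 1 sets the phenotyping sample (variable 8) at 20 per group.

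**The concern.** Two things are unsettled. First, laboratory staff cannot follow both transport descriptions, and the one in Methodology has no money behind it.

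Second, the phenotype endpoint is a change over six months in cells that are frozen and read later. The protocol does not say whether an infant's two samples are read together or apart. Both arrangements attach a laboratory factor to visit: storage time if they are read together, shipment and run if they are read apart. A test that looks only at the before/after change within one arm attributes whatever that factor does to the supplement. If longer storage happened to lower the measured count of a subset, baseline would read low and the follow-up would look like a rise. A rise is what the hypothesis section predicts for CD3, CD4 and natural killer cells. At stake is whether a significant within-group result on these markers can be read as an effect of zinc or iron.

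**Working it through.** **Transport.** The two accounts side by side:

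| Item | Methodology | Facilities Available | Detailed Budget |
|---|---|---|---|
| Transport to Sweden | liquid nitrogen | dry ice, -70° C | dry ice and freight |
| Storage before transport | not stated | -80° C freezer | -83° C freezer |

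The conflict lies in the transport row only. Methodology names no storage condition, so the freezer contradicts nothing.

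**Storage time.** Inputs: enrolment at month t, with t from 0 to 6; baseline draw at t; follow-up draw at t + 6.

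- One batch at month 12 (assumed; the earliest date that includes every follow-up sample). Baseline storage = 12 - t, which is 12, 9 and 6 months for t = 0, 3 and 6. Follow-up storage = 12 - (t + 6) = 6 - t, which is 6, 3 and 0 months. The gap is (12 - t) - (6 - t) = 6 months for every infant. A later batch date lengthens both terms equally and leaves the gap at 6.
- Two batches, at months 6 and 12 (also assumed). Baseline storage = 6 - t and follow-up storage = 6 - t, so the gap is 0. But every baseline sample is then in the first shipment and every follow-up sample in the second.

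**Effect on the tests.** Simulation: 20 infants per group, paired changes normal with SD 1, no treatment effect, the same additive laboratory shift in both arms, two-sided 5% level, 4,000 runs. The shift, in SDs of the paired change, is an assumption; the documents give no value.

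| Shift (SD) | Within-group signed-rank test, % rejecting | Between-arm rank-sum test on change, % rejecting |
|---|---|---|
| 0 | 4 | 4 |
| 0.1 | 7 | 5 |
| 0.2 | 13 | 5 |
| 0.3 | 23 | 5 |
| 0.5 | 55 | 5 |
| 0.8 | 91 | 4 |

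The shift enters the within-group test in full and cancels in the between-arm difference.

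**Which comparison the sample size was built for.** Table 1 sets a control level against a treatment level. Use n per group = 2(z_α/2 + z_β)² s²/d², with s² the mean of the two variances and d the difference in means.

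- CD3: s² = (0.53² + 1.68²)/2 = 1.552 and d = 1.66
- CD4: s² = (0.39² + 1.24²)/2 = 0.845 and d = 1.13
- CD8: s² = (0.17² + 0.54²)/2 = 0.160 and d = 0.63

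Table 1 prints 12, 14 and 9. Two-sided 5% with 90% power and no allowance for loss gives 12, 14 and 9. Two-sided 5% with 80% power gives 9, 11 and 7; dividing by 0.8 for a 20% loss and rounding up gives 12, 14 and 9 as well. The protocol states neither level nor power, so the two cannot be told apart. Both are two-group calculations, so the printed sizes already fit a comparison with control.

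**Cost in precision.** If σ is the SD of the paired change, the standard error within one arm is σ/√20 = 0.224σ. For the difference between two arms it is σ√(2/20) = 0.316σ, larger by a factor of √2 = 1.41.

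**The case against.** The strongest case against the point is that the only thing certain on the page is a drafting conflict over transport. Facilities Available and the budget agree with each other, so one stray phrase in Methodology may be all that needs correcting. The six-month storage gap is written nowhere. It is inferred from one travel line and an undated statement that phenotyping comes later, and the separate freight line leaves room for other shipments. The documents do not show that storage changes the subsets at all, let alone unequally. The trial is randomised and blinded with a placebo arm, and a regression across supplements is already planned.

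Most of this stands, and it limits what may be claimed. A reader might infer that baseline cells are definitely stored six months longer; that holds only for a single batch. A reader might infer that the -80° C freezer conflicts with liquid nitrogen, or that dry ice damages the cells more; the first is not so, and nothing in the documents supports the second. A reader might put a percentage on the spurious change by assuming a monthly loss of cells; the protocol offers no rate to anchor it. A reader might conclude that the trial's phenotype results as a whole are biased; randomisation makes the laboratory difference equal across arms on average, so comparisons with placebo are not.

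What the objection does not remove is the choice of test. The regression is assigned to joint effects of the nutrients, while the effect of zinc or iron alone is assigned to the signed-rank test. Shipping the two time points separately does not rescue that test, because it replaces a storage difference with a run difference.

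**Conclusion.** The point holds in two parts. The contradiction over the transport medium is certain and needs only the text of Methodology and Facilities Available. The statistical part holds under either timing: the named within-group test cannot separate the supplement from a storage or run effect, because the protocol leaves open which of the two is tied to visit.

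The size is unknown. The gap of six months assumes a single batch. The false-positive rates of 13%, 23% and 55% assume shifts of 0.2, 0.3 and 0.5 SD, normal changes, 20 per group and no treatment effect. If the laboratory shift is zero, the within-group test keeps its level, although it still lacks a control. The randomised comparison with placebo is not biased on average by a shift common to all arms. The weakness therefore lies in which analysis carries the conclusion, and the data for a sound one are already within the design.

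**What to change.** 1. Reconcile Methodology, Facilities Available and the Detailed Budget to one transport chain, used for every sample. If it is liquid nitrogen, the budget needs a line for it; if dry ice, Methodology needs one correction. The documents do not settle which is better.
2. State when each time point is shipped and phenotyped. One batch removes the run difference but keeps the storage gap; two batches do the reverse. In either case, balance the five arms within every assay run and record storage days for each sample.
3. In Data Analysis, base the conclusions on CD3, CD4, CD8 and natural killer cells on the between-arm difference in change, each supplement versus placebo. Keep the within-group signed-rank test as description only.
4. Confirm that the placebo arm is phenotyped at both visits in the same number. Table 1 uses a control column, but its note on group size lists only the four supplemented groups.

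The changes are to text, run order and record keeping, and need no further infants, visits or blood volume. If placebo phenotyping is not already planned, it adds 20 × 2 = 40 samples to the assay work. The real downside is precision: the standard error of the between-arm contrast is about 1.41 times that of the within-arm change at the same group size.
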